2.3 Rationale

Since their approval, ESAs have been in wide use in CKD patients both on dialysis and not on dialysis to raise Hb concentrations and reduce the need for RBC transfusions. Because observational studies had shown an association between anemia and increased cardiovascular (CV) morbidity and mortality in ND-CKD patients (Collins, 2003; McClellan et al, 2002; Sarnak et al, 2002; Al Ahmad et al, 2001; Mann, 1999; Levin et al, 1999), clinical trials were conducted in this population to evaluate potential CV benefits of ESAs. Contrary to the hypothesis, 2 large clinical trials did not demonstrate a CV benefit when anemia was treated. The Correction of Hemoglobin and Outcomes in Renal Insufficiency (CHOIR) study evaluated outcomes in subjects with moderate anemia treated with epoetin alfa to Hb concentrations of 13.5 g/dL vs 11.3 g/dL (Singh et al, 2006). The CHOIR study identified an increased risk for death and serious CV events in the higher Hb target arm (hazard ratio 1.34; 95% confidence interval [CI] 1.03 to 1.74), the imbalance being mostly for death and hospitalization for heart failure. The Trial to Reduce Cardiovascular Events with Aranesp® Therapy (TREAT) evaluated ND-CKD subjects with moderate anemia and type 2 diabetes who were randomized to receive either treatment with darbepoetin alfa to a target Hb concentration of 13 g/dL or placebo with rescue darbepoetin alfa therapy if Hb concentration fell < 9 g/dL (Pfeffer et al, 2009). The TREAT study did not demonstrate a benefit on the primary composite CV endpoint of all cause mortality or CV event (hazard ratio 1.05; 95% CI 0.94 to 1.17), however, an increased risk of stroke was observed when compared to the placebo group (hazard ratio 1.92; 95% CI 1.38 to 2.68). The mechanism for the increased risk observed when targeting high Hb concentrations has not been determined. It has been suggested that exposure to high doses, high cumulative dose of ESA, Hb excursions, and rapid Hb rises might contribute to these risks. Thus, there is a desire to define a dosing regimen that can retain the transfusion benefits of ESA treatment while minimizing potential contributing factors listed above. Although in CKD patients ESAs have historically been titrated to achieve a predefined Hb concentration, this may not be the only possible dosing strategy. In particular, a

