10.5.2.2 Secondary Endpoints

Total number of units of RBC transfused per subject will be described for each treatment group, and will be analyzed using a negative binomial regression model which will include the stratification factors used at randomization. As a sensitivity analysis, exposure adjusted event incidence of total number of units RBC transfused will be presented with 95% CI using Chi-square approximation to the Poisson distribution. These analyses will be performed using both on-treatment and on-study approaches.

Time to first RBC transfusion using both on-treatment and on-study approaches will be analyzed by each treatment group with Kaplan-Meier curves, Kaplan-Meier percentiles, the number of subjects censored, and the number of subjects transfused. A supportive analysis will be performed using Cox proportional hazards model ([Cox, 1972](#)) stratified by the stratification factors used at randomization to evaluate the difference between the treatment groups. The hazard ratio and its corresponding 95% CI will be estimated.

Average achieved Hb concentration while receiving investigational product will be described as average Hb using the area under the curve (AUC) method. The median of the difference in achieved Hb concentration (Hodges–Lehmann estimate) between treatment groups will be calculated and 2-sided 95% confidence limits will be derived by using a nonparametric Wilcoxon rank-sum statistic ([Holander and Wolfe, 1973](#)).

Cumulative doses of darbepoetin alfa adjusted for investigation product exposure time will also be summarized, and the median of the difference (Hodges–Lehmann estimate) between treatment groups will be calculated and 2-sided 95% confidence limits will be derived by using a nonparametric Wilcoxon rank-sum statistic.

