10. STATISTICAL METHODS OF ANALYSIS

10.1 General Principles

Descriptive statistics will be presented for all endpoints by treatment group. For continuous variables, these include number of observations, mean, standard error (SE) and/or standard deviation (SD), median, 25th percentile (Q1), 75th percentile (Q3), minimum and maximum. For categorical variables, the frequency and percentage are presented. For time to event endpoints: Kaplan-Meier curves, Kaplan-Meier percentiles, the number of subjects censored, and the number of subjects with events will be summarized. Confidence intervals will be constructed as 2-sided at the 95% level. Summaries of laboratory data, Hb and dose related parameters, and vital signs will be completed using the full analysis set, limited to measurements obtained while the subject is receiving the investigational product.

For variables that are summarized over time, the actual visit for a subject may not exactly coincide with their targeted scheduling. The visit windows defined in [Appendix A](#) will be used to assign evaluations to a most appropriate nominal visit for analysis and summarization.

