10.5.2 Analyses of Secondary Efficacy Endpoint(s)

Total number of units of RBC transfused per subject will be described for each treatment group, and will be analyzed using a negative binomial regression model which will

include the stratification factors used at randomization. As a sensitivity analysis, exposure adjusted event incidence of total number of units RBC transfused will be presented with 95% CI using Chi-square approximation to the Poisson distribution. These analyses will be performed using both on-treatment approach with the full analysis set and on-study approach with all randomized subjects.

Time to first RBC transfusion will be analyzed using both on-treatment approach with the full analysis set and on-study approach with all randomized subjects. It will be analyzed by each treatment group with Kaplan-Meier curves, Kaplan-Meier percentiles and estimates at 6, 12, 18, and 24 months, the number of subjects censored, and the number of subjects transfused. A supportive analysis will be performed using Cox proportional hazards model (Cox, 1972) stratified by the stratification factors used at randomization to evaluate the difference between the treatment groups. The hazard ratio and its corresponding 95% CI will be estimated.

Average achieved Hb concentration while receiving investigational product will be described as average Hb using the area under the curve (AUC) method. The median of the difference in achieved Hb concentration (Hodges–Lehmann estimate) between treatment groups will be calculated and 2-sided 95% confidence limits will be derived by using a nonparametric Wilcoxon rank-sum statistic (Hollander and Wolfe, 1973). As a sensitivity analysis, the above analyses will be repeated excluding Hb concentrations measured within 3 months (84 days) from an RBC transfusion.

Cumulative doses of darbepoetin alfa adjusted for investigation product exposure time (eg, average cumulative darbepoetin alfa dose per 4 week) will also be summarized, and the median of the difference (Hodges–Lehmann estimate) between treatment groups will be calculated and 2-sided 95% confidence limits will be derived by using a nonparametric Wilcoxon rank-sum statistic.

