	Time to First RBC Transfusion by <<Subgroup>>- <<Full Analysis Set>>	Repeat the above analysis by stratification factors, age, gender, race, baseline Hb concentrations, baseline eGFR and diabetes at baseline.
	Time to First RBC Transfusion – <<All Randomized Subjects >>	Repeat of the above analysis using on-study approach.
	Average Achieved Hb Concentration while Receiving Investigational Product – <<Full Analysis Set>>	Summary of the average achieved Hb using the area under the curve method with the median of the difference in achieved Hb concentration (Hodges–Lehmann estimate) between treatment groups, and 2-sided 95% confidence limits by using a nonparametric Wilcoxon rank-sum statistic.
	Average Achieved Hb Concentration while Receiving Investigational Product by <<Subgroup>> – <<Full Analysis Set>>	Repeat the above analysis by stratification factors, age, gender, race, baseline Hb concentrations, baseline eGFR and diabetes at baseline.
	Average Achieved Hb Concentration Excluding Hb within 3 Months from an RBC Transfusion – <<Full Analysis Set>>	Summary of the average achieved Hb using the area under the curve method with the median of the difference in achieved Hb concentration (Hodges–Lehmann estimate) between treatment groups, and 2-sided 95% confidence limits by using a nonparametric Wilcoxon rank-sum statistic. Hb within 3 months from an RBC transfusion will be excluded.
	Average Cumulative Dose of Darbepoetin alfa per 4 Week – <<Full Analysis Set>>	Summary of the average cumulative doses of darbepoetin alfa per 4 week with the median of the difference (Hodges–Lehmann estimate) between treatment groups, and 2-sided 95% confidence limits by using a nonparametric Wilcoxon rank-sum statistic.
	Average Cumulative Dose of Darbepoetin alfa per 4 Week by <<Subgroup>> – <<Full Analysis Set>>	Repeat the above analysis by subgroup of stratification factors, age, gender, race, baseline Hb concentrations, baseline eGFR and diabetes at baseline.
	Average Cumulative Dose of Darbepoetin alfa at Each Study Visit – <<Full Analysis Set>>	Summary of the average cumulative doses of darbepoetin alfa at each study visit.
	Average Cumulative Weight-Adjusted Dose of Darbepoetin alfa at Each Study Visit – <<Full Analysis Set>>	Summary of the average cumulative weight-adjusted doses of darbepoetin alfa at each study visit.

Category	Data/ Endpoint	Description

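### Cumulative dose is contrasted between arms only by a Hodges–Lehmann median difference; no contrast or interval is planned for mean dose

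*SAP*

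**What the plan says.** Cumulative dose is a secondary endpoint (Protocol 10.1.1, SAP 4.2). The secondary objective (Protocol 1.2, SAP 2.2) includes describing its difference between the two strategies.

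- Protocol 10.5.2.2 fixes the method: "Cumulative doses of darbepoetin alfa adjusted for investigation product exposure time will also be summarized, and the median of the difference", by Hodges–Lehmann.
- SAP 10.5.2 repeats it and offers a metric, the average cumulative dose "per 4 week) will also be summarized, and the median of the difference (Hodges–Lehmann estimate) between treatment groups will be calculated". It adds that "2-sided 95% confidence limits will be derived by using a nonparametric Wilcoxon rank-sum statistic".
- The matching table in SAP 12.1 is a "Summary of the average cumulative doses of darbepoetin alfa per 4 week with the median of the difference".

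No difference or ratio of means is planned for dose. Achieved Hb has a sensitivity analysis in SAP 10.5.2; dose has none.

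Within each arm much more is planned. SAP 10.1 covers all endpoints: "For continuous variables, these include number of observations, mean, standard error (SE) and/or standard deviation (SD), median", followed by quartiles and range. SAP 10.5.3 and 10.6.6 add dose by visit, cumulative and weight-adjusted dose, and dose by quartile of initial Hb response. None of these carries a between-arm estimate.

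**The concern.** The two arms are built to have different dose distributions. Under Protocol 6.4.1.2.2 a fixed-dose subject keeps the starting dose, with placebo only after Hb exceeds 12.0 g/dL and until it falls below 10.0 g/dL. Under Protocol Table 1 a titrated subject steps up, steps down or goes to placebo at each visit, up to 300 µg. SAP 6.3 counts placebo as zero dose. Good responders therefore drift below the starting dose and poor responders climb well above it.

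When treatment changes spread and skew as well as location, the median pairwise difference and the difference in means are different quantities. The first responds to how many subjects end up above or below, the second also to how far. Protocol 2.3 raises the second kind of question, noting a suggestion that "exposure to high doses, high cumulative dose of ESA, Hb excursions, and rapid Hb rises might contribute to these risks", and says that a fixed dose could lower cumulative exposure. A reader who takes the Hodges–Lehmann figure as the difference in drug delivered could be misled on one of the named considerations for choosing a regimen.

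**Working it through.** **The plan's own figures.** The documents give no figure for the dose contrast. Their sample size fixes n. At a proportion of 25% and n = 300, the CI width is 2 × 1.96 × √(0.25 × 0.75/300) = 9.80% for one arm and 2 × 1.96 × √(2 × 0.25 × 0.75/300) = 13.86% for the difference. Both are within the stated 10% and 14%. Then 300/0.8 = 375 per arm, as stated.

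**Definitions.** T is the titrated and F the fixed-arm average dose per 4 weeks. Hodges–Lehmann (HL) = median of all T_i − F_j. Mean difference = mean(T) − mean(F), with Welch interval ± 1.96 × √(s_T²/n + s_F²/n).

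**By hand.** Assume an 82 kg subject: 0.45 × 82 = 36.9, rounded down to a 30 µg syringe. Let every fixed subject average 30 µg. The titrated shares and doses below are illustrative.

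- 60% at 15 µg, 40% at 90 µg: mean 0.6 × 15 + 0.4 × 90 = 45, mean difference +15. Of the pairwise differences 60% are −15 and 40% are +60, so HL = −15.
- 60% at 15 µg, 40% at 150 µg: mean 9 + 60 = 69, mean difference +39. HL is still −15.
- 40% at 15 µg, 60% at 90 µg: mean 6 + 54 = 60, mean difference +30. HL = +60.

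HL jumps when the share of escalators crosses one half, and does not register how far the minority escalates.

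**Simulation on the protocol's rules.** From the protocol: Table 1, the fixed-arm hold, the syringe and dose steps, 25 dosing visits, 375 per arm. Assumed: weight N(82, 18) kg; baseline Hb about 9.3 g/dL; steady-state Hb rise E × log2(1 + dose/0.45 µg/kg); E lognormal with the median and log-SD shown. Results are averages over 300 trials per setting, in µg per 4 weeks. Differences can depart from the rounded means by 0.1 to 0.2.

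| E median, log-SD | Final mean Hb T / F | Mean dose T / F | Mean difference (Welch 95% CI) | HL (Wilcoxon 95% CI) | HL CI includes 0 | HL CI wholly below 0 |
|---|---|---|---|---|---|---|
| 0.8, 0.6 | 10.21 / 10.09 | 68.8 / 31.2 | 37.7 (31.4 to 44.0) | 15.0 (10.5 to 20.0) | 0% | 0% |
| 0.8, 1.0 | 10.13 / 10.14 | 74.7 / 29.6 | 45.1 (37.7 to 52.5) | 14.9 (9.2 to 21.7) | 0% | 0% |
| 1.1, 0.6 | 10.22 / 10.30 | 48.0 / 30.5 | 17.4 (12.4 to 22.4) | 1.2 (−1.6 to 4.3) | 86% | 0% |
| 1.1, 1.0 | 10.19 / 10.31 | 57.6 / 28.5 | 29.0 (22.4 to 35.6) | 2.8 (−0.7 to 6.7) | 74% | 0% |
| 1.5, 0.6 | 10.24 / 10.53 | 34.2 / 28.6 | 5.8 (1.9 to 9.7) | −4.8 (−7.0 to −2.5) | 3% | 97% |
| 1.5, 1.0 | 10.24 / 10.47 | 43.2 / 26.5 | 16.7 (11.1 to 22.3) | −2.6 (−5.2 to 0.2) | 57% | 43% |
| 2.0, 1.0 | 10.28 / 10.62 | 34.5 / 24.5 | 10.1 (5.1 to 15.0) | −4.5 (−6.7 to −2.3) | 4% | 96% |

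Check of one interval (1.1, 0.6; SDs 48.6 and 8.9): 1.96 × √((48.6² + 8.9²)/375) = 5.0, so 17.4 ± 5.0. Across settings the SD was 37 to 72 µg under titration and 8.5 to 11.5 under fixed dosing. The Wilcoxon interval covered the median pairwise difference in 90% to 97% of trials and the mean difference in none. The Welch interval covered the mean difference in 94% to 97% and lay above 0 in 100% of trials, except 88% at (1.5, 0.6).

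**Other assumptions.** Two separately built simulations show the same pattern. One (weight 85 ± 20 kg) gave means of 55 against 32 with HL −1, HL −6.5 against a mean difference of +10 in a more responsive population, and HL +14 against +44 in a less responsive one. The other gave 46 against 31 with HL about 0, and 33 against 25 with HL −5.6.

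**Counter-range.** At E 0.3, log-SD 0.6, means were 138.1 and 32.1 (difference 106.0) and HL was 121.2, above the mean difference. At E 2.0, log-SD 0.6, means were 25.2 and 26.6 and HL was −8.3: same sign, and titration did not deliver more. Calibration to equal mean Hb (Protocol 2.3) does not settle it. At E 0.3, log-SD 1.4, final Hb was 9.93 and 9.79, yet HL was 100.5 against a mean difference of 126.0 − 30.5 = 95.5.

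**The case against.** The strongest reply is that nothing is hidden. Per-arm n, mean, SE and/or SD, quartiles and maximum are planned for this endpoint, and a Welch interval could be worked out by hand from n, the means and the SDs (or SEs). Dose by quartile of initial Hb response would show whether poor early responders escalate. The contrast is openly labelled a median of the difference, and a typical-subject comparison is a legitimate choice. The endpoint is secondary, no hypothesis is tested, and the regimen choice rests on several considerations. All of this stands, and it limits the point to one missing estimate and interval.

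Three stronger readings are tempting and are not supported.

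- **That Hodges–Lehmann needs a pure shift to be valid.** It does not; without one it still estimates the median pairwise difference. An opposite sign is opposite only relative to the mean difference.
- **That the Wilcoxon limits are too narrow.** With one arm constant and equal n, the variance of the rank-sum proportion is 0.25/n against 1/(6n) under the null, a ratio of 1.5. Coverage is then 2Φ(1.96/√1.5) − 1 = 89%. But the fixed arm is not constant in µg, because weight, rounding and placebo holds spread it. Simulated coverage was 90% to 97% above, and 90% to 94% in µg (88% to 94% in µg/kg) in the simulation with weight 85 ± 20 kg. The shortfall is modest and not universal.
- **That Hodges–Lehmann must become supplementary.** Which quantity leads is a choice of estimand. The mean has its own weakness: a few subjects near 300 µg can move it.

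**Conclusion.** The point holds as a gap that is cheap to close. The only planned between-arm estimate for cumulative dose can be near zero, or opposite in sign to the mean difference, while titration delivers more drug on average. In the seven tabulated settings the titrated mean was 1.2 to 2.5 times the fixed mean, and HL ran from −4.8 to +15.0 µg against mean differences of 5.8 to 45.1 µg.

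That the two measures can diverge follows from the dosing rules. The size and direction do not: they depend on the Hb-response distribution, which the documents do not give, and some plausible settings show no conflict. The simulation models as specified here also omit early stopping, blood-pressure holds, missed doses and transfusions, each of which could change the dose distributions. Nothing here bears on which dosing strategy is preferable.

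**What to change.** In SAP 10.5.2 and the average-cumulative-dose table of SAP 12.1, add the difference in mean average cumulative dose per 4 weeks with a two-sided 95% CI. Name one method, Welch or bootstrap, and state the direction of subtraction. Give it in µg and in µg per kg of screening weight, a quantity SAP 6.3 already defines. Keep the Hodges–Lehmann estimate and its limits beside it, labelled as the median pairwise difference and not the difference in drug delivered. Record the addition in SAP 11.

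The cost is SAP wording and a row in a planned table, with no new data and no change to dosing. The downside is the mean's sensitivity to a few subjects held near 300 µg, which is the reason to report both.

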10.5.3 Analyses of Exploratory Endpoints

The following exploratory endpoints will be summarized by each treatment group using the full analysis set:

- Darbepoetin alfa dose and weight-adjusted dose received at each study visit
- Hb concentration and its subgroup at each study visit
- Hb concentration change from baseline at each study visit
- Time to first Hb concentration ≥ 10.0 g/dL
- Proportion of Hb measurements ≥ 10.0 g/dL
- Hb rate of change in a 4 week interval at each study visit
- Hb variability at each study visit
- Anti-HLA antibodies as measured using panel reacted antibodies (PRA) over time based on both on-treatment and on-study approaches

Anti-HLA antibodies over time will be summarized by the transfusion subgroup (on-treatment approach) and by randomized treatment group using the full analysis set. The summary will be repeated by the transfusion subgroup (on-study approach) and by randomized treatment group using all randomized subjects.

Furthermore, the following Hb-related information will be evaluated and summarized by randomized treatment group using the full analysis set

- At least one Hb < 8.0 g/dL and the proportion of the Hb measurements < 8.0 g/dL
- At least one Hb < 9.0 g/dL and the proportion of the Hb measurements < 9.0 g/dL
- At least one Hb > 11.0 g/dL and the proportion of the Hb measurements > 11.0 g/dL
- At least one Hb > 12.0 g/dL and the proportion of the Hb measurements > 12.0 g/dL
- At least one Hb > 13.0 g/dL and the proportion of the Hb measurements > 13.0 g/dL

Number of days hospitalized will be summarized by treatment group using the on-treatment approach and the full analysis set. As a sensitivity analysis, the number of days hospitalized will also be summarized by treatment group using the on-study approach and all randomized subjects.

Initial Hb response at Week 5 will be summarized by treatment group using initial Hb response analysis set. The following will be summarized by initial Hb-response subgroup and treatment group using the initial Hb response analysis set:

- Hb concentration at each study visit and the achieved Hb
- Darbepoetin alfa dose at each study visit and the cumulative dose

Subjects received ≥ 1 RBC transfusion and time to first RBC transfusion will be descriptively summarized by the initial Hb response subgroup using on-treatment approach.

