7.1.3 Study Day 1 Evaluations

The Day 1 visit will be the same day as screening Visit 2. After completion of the screening period, when the subject has met all eligibility criteria, sites will need to complete the randomization call in the IVR/IWR system prior to beginning the Day 1 evaluations. All subsequent doses and study visits will be scheduled based on the Day 1 date.

The following procedures will be completed on Day 1:

- Medical and surgical history, including history of transfusions
- Physical exam, including height and weight
- Electrocardiogram
- Concomitant medications (as specified in [Section 7.2.9](#))
- eGFR, serum creatinine
- Complete blood count (CBC; results will remain blinded)
- TSAT, ferritin, iron, TIBC
- Troponin-T
- Serum albumin, high sensitivity C-reactive protein (CRP)
- Reticulocytes (results will remain blinded)
- Blood samples for biomarkers
- Spot urine albumin and creatinine
- Anti-erythropoietic protein antibodies
- Anti-human leukocyte antigen (HLA) antibodies
- Investigational product administered

Once the subject is enrolled, collection of the following will begin:

- RBC transfusions, as well as transfusions of other blood-derived products
- Endpoint data for adjudication
- Hospitalizations, including observational stays, and emergency department visits
- Adverse events

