7.3.2 Anti-HLA Antibodies

Samples for assessment of allosensitization will be collected. Allosensitization is the development of an immune response against foreign antigens, and in particular foreign HLA. The detection of anti-HLA antibodies (allosensitization) has changed dramatically over the last few years, becoming much more sensitive and more specific ([Murphey and Forsthuber, 2008](#)). Given the rapid innovation in the determination of allosensitization, samples collected for anti-HLA antibodies during the course of the trial will be stored until the completion of the study. Anti-HLA antibodies will then be measured using the state-of-the-art and accepted methods at that time.

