10.5.2.4 Exploratory Endpoints

All exploratory endpoints, except otherwise mentioned in this section, will be described by each treatment group. In addition to Hb concentration and change from baseline at each study visit, the subgroups of Hb concentrations, will also be presented.

Number of days hospitalized will be summarized by treatment group using the on-treatment approach.

Achieved Hb concentration and cumulative dose over time will be summarized by the initial Hb responsiveness and treatment group.

Anti-HLA antibodies over time will be tabulated by each treatment group.

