2.4 Exploratory

To describe with each dosing strategy:

- Dose and Hb-related parameters
- Initial Hb response and resulting dose and achieved Hb
- Duration of hospitalization
- Allosensitization over time

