	Darbepoetin alfa Dose Received at Each Study Visit – <<Full Analysis Set>>	Summary of the darbepoetin alfa dose received at each study visit by treatment group.
	Darbepoetin alfa Weight-adjusted Dose Received at Each Study Visit – <<Full Analysis Set>>	Summary of the darbepoetin alfa weight-adjusted dose received at each study visit by treatment group.
	Hb Concentration at Each Study Visit – <<Full Analysis Set>>	Summarize the Hb concentration and its subgroup at each study visit by treatment group.
	Hb Concentration Change from Baseline at Each Study Visit – <<Full Analysis Set>>	Summarize the Hb concentration change from baseline at each study visit by treatment group.
	Time to First Hb Concentration ≥ 10.0 g/dL – <<Full Analysis Set>>	Summary of the time to first Hb concentration ≥ 10.0 g/dL by treatment group.
	Proportion of Hb Measurements ≥ 10.0 g/dL – <<Full Analysis Set>>	Summarize the proportion of Hb measurements ≥ 10.0 g/dL by treatment group in the <<Full Analysis Set>>.
	Hb Rate of Change in a 4 Week Interval at Each Study Visit – <<Full Analysis Set>>	Summary the Hb rate of change in a 4 week interval at each study visit by treatment group.
	Hb Variability at Each Study Visit – <<Full Analysis Set>>	Summary of the Hb variability at each study visit by treatment group.
	Anti-human Leukocyte Antigen (HLA) Antibodies over Time – <<Full Analysis Set>>	Summarize the anti-human leukocyte antigen (HLA) antibodies over time by treatment group using on-treatment approach.
	Anti-human Leukocyte Antigen (HLA) Antibodies over Time – <<All Randomized Subjects>>	Summarize the anti-human leukocyte antigen (HLA) antibodies over time by treatment group using on-study approach.
	Anti-human Leukocyte Antigen (HLA) Antibodies over Time by Transfusion Subgroup – <<Full Analysis Set>>	Summarize the anti-human leukocyte antigen (HLA) antibodies over time by transfusion subgroup and treatment group using on-treatment approach.
	Anti-human Leukocyte Antigen (HLA) Antibodies over Time by Transfusion Subgroup – << All Randomized Subjects >>	Summarize the anti-human leukocyte antigen (HLA) antibodies over time by transfusion subgroup and treatment group using on-study approach.

Category	Data/ Endpoint	Description

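### Anti-HLA results are summarized by visit with no within-subject comparison to Day 1, so new sensitization is not separated from prior sensitization, above all in the transfusion-subgroup tables.

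*SAP*

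**What the plan says.** The exploratory objective (Protocol 1.4, SAP 2.4) is to describe "Allosensitization over time" with each dosing strategy. Protocol 7.3.2 uses the term in two ways. It first says "Allosensitization is the development of an immune response against foreign antigens, and in particular foreign HLA", which is an event in a subject. It then says "The detection of anti-HLA antibodies (allosensitization) has changed dramatically over the last few years", which equates the word with finding the antibody.

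Samples are taken on Day 1 (Protocol 7.1.3), every 12 weeks (7.1.4.1) and at the end of study (7.1.7). They are stored and assayed only when the study is complete, by the methods accepted at that time (7.3.2).

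The planned analyses are all summaries by visit:

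- Protocol 10.5.2.4: "Anti-HLA antibodies over time will be tabulated by each treatment group".
- SAP 10.5.3: panel reactive antibodies (PRA) over time by arm, on-treatment and on-study. For the subgroups: "Anti-HLA antibodies over time will be summarized by the transfusion subgroup (on-treatment approach) and by randomized treatment group using the full analysis set", repeated on-study in all randomized subjects.
- SAP 12.1: "Summarize the anti-human leukocyte antigen (HLA) antibodies over time by treatment group using on-treatment approach", with matching tables for the on-study approach and the transfusion subgroups.

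SAP Appendix A gives anti-HLA its own visit windows, starting with Week 1 (planned day 1, study days 1 to 43).

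**The concern.** If allosensitization means developing an antibody, it is measured by comparing each subject with that subject's own starting status. None of the planned outputs does this. There is no conversion endpoint, no change from Day 1, no split by Day 1 status and no PRA positivity rule.

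The SAP makes such comparisons elsewhere. Section 10.5.3 asks for hemoglobin change from baseline, and Section 10.6.5 lists baseline and post-baseline status for anti-erythropoietic antibodies.

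Prior exposure is possible in this population. Transfusion is excluded only within 8 weeks of screening and during screening (Protocol 4.2), and transfusion in the preceding 12 months is a stratification factor (5.2). Some subjects may therefore be positive at Day 1.

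The transfusion subgroups (none, one, more than one event; SAP 6.3) are defined by what happens after randomization, so nothing balances their Day 1 status. They are also the tables that bear on the risk raised in Protocol 2.1, that transfusion may cause allosensitization. A difference in starting status could be read there as an effect of transfusion.

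**Working it through.** The documents give no anti-HLA prevalence, conversion rate, cut-off or precision, so there is no figure to reproduce. Every rate below is an assumption, used to show what a by-visit table can and cannot reveal.

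**1. Is Day 1 in the tables?** Appendix A picks the measurement closest to the planned day, so a Day 1 sample fills the Week 1 row. However, the appendix introduces its windows as applying to measurements after baseline, so the intended role of that row is unclear. Taken at face value, the tables show Day 1 status at group level.

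**2. How mixed are the later rows?** Let b be Day 1 positivity and i the conversion among Day 1 negatives, with no reversion.

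- Later prevalence = b + (1 − b)i
- Share of later positives already positive at Day 1 = b / [b + (1 − b)i]

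| b | i | Later prevalence | Share already positive at Day 1 |
|---|---|---|---|
| 5% | 20% | 0.05 + 0.95 × 0.20 = 24.0% | 0.05/0.24 = 21% |
| 20% | 5% | 0.20 + 0.80 × 0.05 = 24.0% | 0.20/0.24 = 83% |
| 40% | 2% | 0.40 + 0.60 × 0.02 = 41.2% | 0.40/0.412 = 97% |

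The first two cases give the same later prevalence with opposite make-up. The Week 1 row would tell these two apart, but it does not resolve steps 3 and 4.

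**3. Does a Day 1 row plus a later row identify conversion?** Allow reversion r among Day 1 positives. Then i = [later prevalence − b(1 − r)] / (1 − b). For an observed move from 20% to 22%:

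- r = 0: (0.22 − 0.20)/0.80 = 2.5%
- r = 10%: (0.22 − 0.18)/0.80 = 5.0%
- r = 20%: (0.22 − 0.16)/0.80 = 7.5%
- r = 30%: (0.22 − 0.14)/0.80 = 10.0%

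The same two rows fit a fourfold range of conversion.

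**4. Do the rows cover the same subjects?** Not necessarily. Investigational product stops at dialysis or transplant, and subjects may leave the study (Protocol 8.1). On-treatment follow-up is cut at the last dose plus 84 days (SAP 6.3), and missing values are not imputed (SAP 9.3.2). Suppose 25% are positive at Day 1, no one's status changes, and 40% of positives and 20% of negatives have no later sample. The positives left are 0.25 × 0.60 = 0.15 and the negatives left are 0.75 × 0.80 = 0.60. Prevalence becomes 0.15/0.75 = 20%, a 5-point fall with no antibody change.

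**5. Transfusion subgroups.** Assume Day 1 positivity of 30% in one subgroup and 10% in the other, with 5% conversion in both.

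- Later rows: 0.30 + 0.70 × 0.05 = 33.5% and 0.10 + 0.90 × 0.05 = 14.5%, a gap of 19 points
- Week 1 row: a gap of 20 points
- New positivity among Day 1 negatives: 5% and 5%, a gap of 0

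With equal Day 1 positivity the later gap would be 0. In addition, the subgroup label covers the whole evaluation period (SAP 6.3), so visits before a subject's first transfusion are still counted under the transfused label.

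**6. Precision of a new-positive comparison.** With 375 per arm and an assumed 25% positive at Day 1, about 375 × 0.75 = 281 per arm are Day 1 negative. At 5% conversion, the 95% half-width of the difference between arms is 1.96 × √(2 × 0.05 × 0.95/281) = 3.6 points. If arms differed by 5 points in transfusion and 20% to 30% of those transfused were sensitized, the arm difference would be 0.05 × 0.20 = 1.0 to 0.05 × 0.30 = 1.5 points. The comparison would not resolve that.

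**The case against.** A reader might infer that the tables ignore Day 1 altogether. They do not: Appendix A provides a Week 1 row, and a subgroup table reading 30% and 10% in that row would show that the gap preceded treatment. This objection stands. What the row cannot do is link each subject's later result to the first one (steps 3 and 4).

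A reader might also infer that the tables show prior sensitization instead of new, or that the objective cannot be answered. Neither is supported. Later rows contain both kinds. The objective is only to describe, the listed endpoint is simply anti-HLA antibodies, and Protocol 7.3.2 also uses the term for detection. A table by visit is a legitimate partial description.

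Nor do the documents support systematic bias between the arms. Randomization is stratified by transfusion in the preceding 12 months, and a history of organ transplant is excluded (Protocol 4.2.9). Dilution and chance imbalance remain.

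It is tempting to add that subjects transfused before the study are more likely to be transfused during it. The documents do not say so, which is why the point is only that the subgroups may differ at Day 1.

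Finally, one can object that this is a single exploratory endpoint in a study with no hypothesis test, that it is not among the considerations named for choosing a regimen (Protocol 2.3), and that no assay-specific cut-off could be written while the assay choice is deferred. All of that limits the weight of the point and sets the timing of the fix. It does not remove the gap.

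**Conclusion.** The concern holds in a limited form. The plan specifies anti-HLA summaries by visit, with a Week 1 row that appears to carry Day 1, but no within-subject comparison with Day 1. Later rows mix prior with new sensitization and cannot separate conversion from reversion or from a changing set of subjects. The consequence is most serious in the transfusion-subgroup tables, where starting status is not protected by randomization.

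The size is unknown because the documents give no anti-HLA rates. Under the assumed ranges (Day 1 positivity 5% to 40%, conversion 2% to 20%, no reversion), between 21% and 97% of later positives would already have been positive at Day 1. The 19-point subgroup gap depends on the assumed 30% and 10% starting rates and vanishes if they are equal.

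This is a modest, worthwhile correction to an exploratory, descriptive endpoint. It makes the result interpretable; it does not give the study power to detect a small difference between arms.

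**What to change.** In SAP 10.5.3 and the table list in 12.1:

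1. Set a PRA positivity rule once the assay is chosen and before the stored samples are assayed.
2. Add the proportion newly positive among Day 1 negative subjects, by visit and at any time, with the between-arm difference and its 95% CI. Show the number with evaluable samples at each visit.
3. For Day 1 positive subjects, report change in PRA from Day 1.
4. Apply the same split by Day 1 status to the transfusion-subgroup tables, and keep them descriptive, since the groups form after randomization.
5. In Appendix A, state that the anti-HLA Week 1 row is the Day 1 baseline, and reconcile this with the sentence introducing the windows as post-baseline.

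The existing by-visit tables can stay. No new samples or visits are needed. The cost is a few extra tables, a positivity rule agreed in time, and a smaller denominator for the new-positive analysis, because Day 1 positive subjects leave it.
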